11.1 TOXICITIES/SIDE EFFECTS

Risks

⁶⁸Ga-RM2 PET/CT Scans

As part of this scan there is radiation delivered from the ⁶⁸Ga and from the low dose CT scan that are performed as part of the PET/CT for attenuation correction and co-registration. Although any exposure to ionizing radiation has the potential to cause some harm to tissue, the radiation exposures in this study are comparable to the low-level exposures associated with common diagnostic procedures such as CT scanning. There remains a low theoretical risk of developing a cancer at some point later in life as a result of the radiation exposure received in this study. This risk is much smaller than the clinical risks posed by the patient's current cancer. Participants should not father a baby while on this study. Acceptable birth control methods include abstinence, double barrier method, surgically sterilized patient or partner.

RM2

A recent study of ⁶⁸Ga-RM2 in 5 normal male volunteers reported no drug related adverse effects after administration of up to 28 µg ⁶⁸Ga-RM2 (26). There were also no drug related adverse effects in a study of 14 patients with prostate cancer imaged with ⁶⁸Ga-RM2 (27). Other non-radioactive GRPr antagonists have been studied for treatment of prostate cancer and were well tolerated at several degrees of magnitude higher doses. In a phase I study the GRPr antagonists RC3095 was administered at doses ranging from 8-96 µg/kg once or twice daily, i.e. approximately 560 µg/day – 13440 µg/day. In this study the only discomfort observed was local discomfort at the injection site.

There is a potential small risk of infection at the site of injection.

Radiation Dosimetry

⁶⁸Ga-RM2 Radiation Doses in the 70-kg Standard Man

⁶⁸ Ga Administered Activity:	200	MBq
# of 80-mA CT scans:	1	
Organ dose per 80-mA CT scan:	9	mSv

Absorbed Dose s

	⁶⁸ Ga-RM2		⁶⁸ Ga-RM2+CT
	mSv/MBq	mSv/scan	mSv
Adrenals	0.011	2.2	11.2
Brain	0.0056	1.12	10.12
Gallbladder Wall	0.011	1.2	10.2
LLI Wall	0.014	2.2	11.2
Small Intestine	0.01	2.8	11.8
Stomach Wall	0.038	2	11
ULI Wall	0.0094	7.6	16.6
Heart Wall	0.028	1.88	10.88
Kidneys	0.081	5.6	14.6
Liver	0.023	16.2	25.2
Lungs	0.0071	4.6	13.6
Muscle	0.0082	1.42	10.42
Pancreas	0.51	1.64	10.64
Red Marrow	0.013	102	111
Osteogenic Cells	0.013	2.6	11.6
Skin	0.022	2.6	11.6
Spleen	0.006	4.4	13.4
Testes	0.023	1.2	10.2
Thymus	0.01	4.6	13.6
Thyroid	0.007	2	11
Urinary Bladder Wall	0.027	122	131
Total Body	0.61	2	11
Effective Dose (mSv/MBq)	0.051	10.2	19.2

Table 3. ^{68}Ga -RM2 absorbed Doses in 70-kg Standard Man per MIRD (OLINDA) Formalism Based on data from 5 volunteers. The calculations assume a bladder voiding interval of 3.5 h (26). Effective dose would be reduced by 25% by frequent bladder voiding (1h interval).

Assessment for Toxicity

Safety Outcome Measures (CTCAE v4)

Infusion Reaction

Patients will be monitored during and after ^{68}Ga -RM2 infusion for 120 minutes after the infusion. The safety and tolerability of ^{68}Ga -RM2 will be assessed using the following primary safety outcome measure:

- Incidence, nature, and severity of adverse events up to 1 day following peptide administration.
- Change in vital signs during administration

12.0 CRITERIA FOR THERAPEUTIC RESPONSE/OUTCOME ASSESSMENT

Tumor response will not be assessed as part of the study.

13.0 CRITERIA FOR REMOVAL FROM STUDY

Participation in the study is strictly voluntary. Patients have the right to withdraw from the study at any time. If a patient chooses to withdraw, he or she must inform the investigator immediately. In addition, the investigator has the right to terminate participation of any patient at any time if it is deemed in the patient's best interest. The reason and circumstances for premature discontinuation will be documented in the patient's medical records. Possible examples for reasons of premature study withdrawal include withdrawal of consent, SAE or intolerable AE, or any other medical illness at investigator's discretion.

14.0 BIOSTATISTICS

Accrual Rate

The Urology Service performs on average 600-700 radical prostatectomies per year of which patients with intermediate or high-risk disease represent the majority. This imaging study does not compete with therapeutic studies and there is also no competing imaging study for primary prostate cancer. Therefore, we expect an accrual rate of one patient per week.

Primary objective (specific aim 1)

The primary objective of this proposal is to estimate the sensitivity and specificity of PET using a gastrin releasing peptide receptor antagonist for localizing tumors of the prostate. Localization will be

defined using a total of 12 regions within the prostate: right and left base, midgland and apex in both peripheral and transition zones. The uptake on each region will be assessed by a radiologist blinded to standard of care imaging and clinical characteristics. Histopathological confirmation will be used as the gold standard.

Unit of analysis will be region and the correlation between regions of the same prostate will be handled statistically using a variance inflation factor (VIF) as described before (44). Primary analysis will involve an ROC curve for the uptake and calculation of the area under it. We will also report sensitivity and specificity in selected operating points from the ROC curve. With 20 patients and a total of 240 regions we will be able to estimate the sensitivity to within approximately +/- 11.4% and specificity to within +/- 8.1% with 95% confidence. These calculations are informed by a recent investigation of the use of 3T DW-MR imaging for the same disease at our institution (29). Specifically we used presumed values of 65% and 80% for sensitivity and specificity respectively, a VIF of 1.22 and a region-based prevalence of 40% which corresponds to approximately 100 tumor-bearing regions.

Secondary objective 1 (specific aim 2)

We will construct ROC curves separately for PET and MR, based on blinded five-point scale readings using histopathology as the gold standard. Curves will be compared using the Obuchowski method adjusted for clustering. We will also dichotomize the readings (0 and 1 as negative, and 2 or up as positive) and compare sensitivity and specificity of standard of care MR imaging with PET using a McNemar's test adjusted for multiple regions. The same comparisons will also be made for the joint analysis of PET and MR imaging vs. PET alone and MR imaging alone, respectively.

With 20 patients contributing 12 regions each we will have approximately 80% power to detect an absolute difference of 10% (e.g. 65% vs 75%) between the sensitivities and specificities (45) while controlling the Type I error rate at 5%.

Secondary objective 2 (specific aim 2)

Because of the limited knowledge on the relationship between uptake of ⁶⁸Ga-RM2 on the hand and AR signaling and ETS rearrangements on the other hand, we will perform descriptive, hypothesis generating analyses for this aim. Specifically, we will determine the ⁶⁸Ga-RM2 SUVs for tumors with and without ETS rearrangement, AR amplification, AR gene expression signature, and PTEN loss in a descriptive fashion. We will also study the relationship between SUVs and semiquantitative immunohistochemical parameters, such as GRPr and nuclear AR expression levels using Spearman rank correlation.

Exploratory analyses

Detection of lymph node metastases

The frequency of lymph node and distant metastases in the studied patient population is expected to be small (a total of 20 patients will be studied, only 6 of whom will be high risk patients). Therefore, sensitivity and specificity for detection metastatic disease will only be recorded in a descriptive way and not further analyzed.

Safety and tolerability of ⁶⁸Ga-RM2

The safety and tolerability of ^{68}Ga -RM2 will be assessed using the following primary safety outcome measures: Incidence and nature of DLTs; incidence, nature, and severity of adverse events; and change in vital signs and clinical laboratory results. Incidence and severity of DLTs and adverse events will be estimated with sample proportions and 95% confidence intervals while changes in vital signs and laboratory parameters will be tested using the signed-ranks test and summarized with descriptive statistics.

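### The planned precision for sensitivity and specificity does not follow from the stated variance inflation factor of 1.22; the stated half-widths imply about 1.49

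*Combined protocol and SAP*

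**What the plan says.** Section 14.0, under the primary objective (specific aim 1), takes the prostate region as the unit of analysis, with 12 regions per patient. Correlation between regions of the same prostate is to be handled with a variance inflation factor, by reference to a cited methods paper. The precision statement, for 240 regions in 20 patients, then reads: "we will be able to estimate the sensitivity to within approximately +/- 11.4% and specificity to within +/- 8.1% with 95% confidence".

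The inputs follow in the same paragraph: "presumed values of 65% and 80% for sensitivity and specificity respectively", together with "a VIF of 1.22 and a region-based prevalence of 40% which corresponds to approximately 100 tumor-bearing regions". They are said to be informed by an earlier diffusion-weighted MRI study at the same institution. No formula is given for the half-widths, and the section does not say whether 1.22 multiplies the variance or the standard error.

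**The concern.** A variance inflation factor, by its name, multiplies the variance, so it widens a confidence interval by its square root. The square root of 1.22 is 1.105, so clustering should widen the intervals by about 10%. The stated half-widths are about 22% wider than the unclustered ones, as if the whole factor had been put on the standard error.

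This is the only precision statement for the primary objective. As written, the reader cannot tell how much information the plan assumes:

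- At a VIF of 1.22, the effective numbers of regions are 100/1.22 = 82 tumor-bearing and 140/1.22 = 115 tumor-free.
- At a VIF of 1.49, they are about 67 and 94.

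The same factor is the plan's stated way of handling clustering in the analysis. If it were put on the standard error there too, with a true VIF of 1.22, the reported intervals would be about 10% too wide.

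**Working it through.** **Inputs (all from Section 14.0, primary objective).** Sensitivity 0.65; specificity 0.80; VIF 1.22; 95% confidence, so z = 1.96; 240 regions, of which about 100 bear tumor, leaving about 140. Exactly 40% of 240 is 96, leaving 144.

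**Step 1. Reproduce the stated figures.** Put 1.22 on the standard error, with 100 and 140 regions: half-width = 1.22 × 1.96 × sqrt(p(1−p)/n).

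- Sensitivity: 1.22 × 1.96 × sqrt(0.65 × 0.35/100) = 1.22 × 9.35% = 11.41%
- Specificity: 1.22 × 1.96 × sqrt(0.80 × 0.20/140) = 1.22 × 6.63% = 8.08%

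Both agree with the stated 11.4% and 8.1%.

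**Step 2. Put 1.22 on the variance.** Half-width = 1.96 × sqrt(1.22 × p(1−p)/n).

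| | Regions | No clustering | 1.22 on variance | 1.22 on standard error | Stated |
|---|---|---|---|---|---|
| Sensitivity | 100 | 9.35% | 10.33% | 11.41% | 11.4% |
| Specificity | 140 | 6.63% | 7.32% | 8.08% | 8.1% |
| Sensitivity | 96 | 9.54% | 10.54% | 11.64% | 11.4% |
| Specificity | 144 | 6.53% | 7.22% | 7.97% | 8.1% |

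At 100/140 the ratios of stated to computed are 11.4/10.33 = 1.104 and 8.1/7.32 = 1.107, against sqrt(1.22) = 1.105.

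**Step 3. Solve back for the VIF.** Implied VIF = (h/1.96)² × n/(p(1−p)), where h is the stated half-width. The ranges allow for rounding of h to one decimal.

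- Sensitivity, n = 100: 1.487 (1.474 to 1.500)
- Specificity, n = 140: 1.494 (1.476 to 1.513)

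Both ranges contain 1.22² = 1.488 and exclude 1.22. With 96/144 the ranges are 1.415 to 1.440 and 1.518 to 1.556. These do not overlap, so no single VIF gives both figures, and 100/140 are the counts that fit.

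**Step 4. Try other interval methods with 1.22 kept on the variance (n = 100/140).**

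| Method | Sensitivity | Specificity |
|---|---|---|
| t on 19 df | 11.0% | 7.8% |
| Continuity correction | 10.9% | 7.8% |
| Clopper-Pearson on effective n, mean half-width | 10.8% | 7.7% |
| Wilson on effective n | 10.1% | 7.3% |
| Stated | 11.4% | 8.1% |

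The longer arm of the asymmetric intervals was also tried, at 100/140 and at 96/144. Some versions match one stated figure: continuity-corrected Wilson gives 11.4% with 8.7% at 100/140, and Wilson gives 11.0% with 8.1% at 96/144. None matches both.

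**The case against.** The best defense is that the half-widths do follow from the stated inputs by one simple rule, 1.22 on the standard error. The papers behind the VIF method and its value are not available here, so 1.22 may be a standard-error ratio in its source. That is fair, and it is why the cause is left open. It does not rescue the text: if 1.22 is such a ratio, it is not the variance inflation factor that the plan calls it.

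A second argument is that little depends on the difference. The aim is estimation, with no target precision, success threshold or test on sensitivity or specificity. On either reading the half-widths are correct or conservative. The other assumptions are also looser than the discrepancy. Section 3.4.6 reports 88% sensitivity for this tracer, and at that value the half-width would be 1.96 × sqrt(1.22 × 0.88 × 0.12/100) = 7.0%, a shift of more than 3 points. This stands as a limit on practical importance, but loose assumptions do not excuse a result that fails to follow from them.

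Third, the sensitivity figure is marked as approximate. That does not cover a one-decimal figure that is 1.1 points off, and the specificity figure carries no such qualifier.

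**Conclusion.** The point holds: the precision statement is wrong as written. With 100 and 140 regions and 1.22 as a true VIF, the half-widths should be about 10.3% and 7.3%, so the stated figures are too wide by 1.1 and 0.8 percentage points. If the stated half-widths are right, the VIF is about 1.49, which is 22% more variance than the stated factor allows (1.49/1.22 = 1.22).

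This rests on normal-approximation intervals, the region counts that fit the stated figures, and the ordinary meaning of a variance inflation factor. The documents do not show which number is at fault. If 1.22 is a true VIF, the error is conservative; if it is a standard-error ratio, the half-widths stand and the clustering is understated on paper. Neither case makes the sample of 20 patients inadequate on this account, and nothing here bears on the power statement for the McNemar comparison.

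**What to change.** Check the source of 1.22, then correct one of the two numbers in Section 14.0:

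- **If 1.22 is a VIF:** restate the precision as about +/- 10.3% for sensitivity and +/- 7.3% for specificity (100 and 140 regions, 1.22 applied to the variance). If exactly 40% of 240 is used, the figures are 10.5% and 7.2%.
- **If 1.22 is a standard-error ratio:** keep 11.4% and 8.1%, and state the VIF as about 1.49.

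In either case, show the formula and the region counts. It would also help, though the correction does not depend on it, to say that in the analysis the VIF is estimated from the trial's own data and applied to the variance. The cost is a one-sentence correction plus the formula, with no change to the design or sample size.

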PET/CT. The reader will record the level of suspicion for the presence of cancer in each sextant of the peripheral and transition zones using a 5-point index scale. The minimum intensity of uptake for a positive lesion (score > 1 on the 5 point scale) will be defined as mean uptake in normal prostate tissue plus two-times the standard deviation in prostate tissue without focal radiotracer uptake. Mean and maximum standardized uptake values will be recorded for each suspicious focus on PET. We will use ROC analysis to determine the sensitivity/specificity for prostate cancer detection by various visual scores and quantitative thresholds for lesion —positivity. Quantitative thresholds will be based on SUVs as well as lesion-to-background ratios. In addition to this analysis of the prostate, focal ⁶⁸Ga-RM2 uptake in lymph nodes, bones or other organs that is not explained by the normal biodistribution will be recorded.

MRI. Standard of care MRI studies at the Department of radiology are performed using a 3T whole-body unit. Transverse T1-weighted and transverse, coronal, and sagittal T2-weighted fast spin-echo sequences are obtained. Diffusion-weighted MRI is acquired in the transverse plane using a single shot spin-echo echo-planar imaging sequence with multiple b-values (b 0-1000). Dynamic contrast-enhanced MRI is performed using a transverse 3D T1-weighted spoiled gradient-echo sequence with a temporal resolution <7 seconds. Images are acquired after i.v. injection of 0.1 mmol/kg body weight gadolinium-DTPA at a rate of 2 mL/s. Based on these images the likelihood of prostate will be scored on a 5-point scale as described in several previous publication of the Department of Radiology, for example (29).

Joint analysis of PET and MR images. Following this independent reading of the MRI and PET images, a joint reading of PET and MR will be performed. This will allow us to localize the findings on PET to the prostate zonal anatomy on MRI. We will then also record the likelihood of cancer in each prostate region but now based on the combined information from the PET and MRI. This analysis is performed in order to evaluate if the combination of PET and MR imaging is more accurate than PET and MR alone. Since combined PET/MR scanners have recently been introduced it is clinically relevant to evaluate if the combination of ⁶⁸Ga-RM2-PET and MR is potentially more accurate for detection of prostate cancer than either ⁶⁸Ga-RM2-PET/CT or MR alone.

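### The stated 80% power for a 10-point PET vs MRI difference is unsupported for sensitivity: on the 96-100 tumor-bearing regions it needs almost nested readings, and no discordance is given

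*Combined protocol and SAP*

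**What the plan says.** Section 14.0, Secondary objective 1 (specific aim 2), plans to "compare sensitivity and specificity of standard of care MR imaging with PET using a McNemar's test adjusted for multiple regions". The plan repeats this for the joint PET and MR reading against each modality alone. The power statement follows: "With 20 patients contributing 12 regions each we will have approximately 80% power to detect an absolute difference of 10% (e.g. 65% vs 75" (the last figure is also a percentage). It applies this one figure to sensitivity and specificity alike, sets the type I error at 5%, and cites reference 45 for the method.

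The only inputs that could feed this figure stand under the primary objective in the same section, where they support the precision of a single modality: presumed sensitivity 65% and specificity 80%, "a VIF of 1.22 and a region-based prevalence of 40% which corresponds to approximately 100 tumor-bearing regions". The precision quoted there is to "estimate the sensitivity to within approximately +/- 11.4% and specificity to within +/- 8.1% with 95% confidence".

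Section 10.0 (Image data analysis) has PET and MRI read by different readers, each blinded to the other test. The combined reading comes afterwards: "Following this independent reading of the MRI and PET images, a joint reading of PET and MR will be performed".

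**The concern.** The power of McNemar's test depends on how often the two tests disagree, and the plan states no discordance rate or between-test correlation. It also does not say whether the 5% is one- or two-sided. One figure covers two comparisons with different denominators: sensitivity is compared only in tumor-bearing regions and specificity only in tumor-free ones. The sentence speaks of 20 patients with 12 regions each, that is 240 regions, and neither comparison uses all of them.

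This is the plan's only statement of what the McNemar comparison of PET and MRI can detect. If the true power for sensitivity is nearer one half, a non-significant result could be misread as evidence from a comparison with 80% power.

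**Working it through.** **Inputs.** From Section 14.0: 240 regions; prevalence 40%, so 0.40 × 240 = 96 tumor-bearing regions (the plan rounds to about 100) and 140-144 tumor-free; difference d = 0.10; type I error 5%; VIF 1.22. Discordance ψ is not given and is treated as unknown.

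**How the plan uses 1.22.** Its precision figures reproduce when 1.22 multiplies the standard error:
- 1.96 × √(0.65 × 0.35/100) × 1.22 = 11.4%
- 1.96 × √(0.80 × 0.20/140) × 1.22 = 8.1%

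With 1.22 inside the root they would be 10.3% and 7.3%. Using 1.22 for a paired difference is in either case an assumption, because the plan gives it for one modality. Results are therefore shown for V = 1 (no clustering), V = 1.22 (on the variance) and V = 1.22² = 1.488 (on the standard error).

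**The plan's 80%.** It cannot be reproduced without ψ. The question is which ψ would give it.

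**Formula.** Power = Φ[(d√(n/V) − z√ψ)/√(ψ − d²)], with z = 1.96 two-sided or 1.645 one-sided. Since the two discordant cells differ by d, ψ cannot be below 0.10.

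Example: n = 96, V = 1, ψ = 0.20, two-sided. (0.10 × √96 − 1.96 × √0.20)/√0.19 = (0.980 − 0.877)/0.436 = 0.237, so power is 59%.

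**Largest discordance that still gives 80% power, sensitivity, n = 96-100.** Enumeration is of the uncorrected McNemar test on n/V effective pairs.

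| | V = 1 | V = 1.22 | V = 1.488 |
|---|---|---|---|
| Two-sided, normal approximation | 12.5-13.0% | 10.3-10.7% | none (73-75% at ψ = 10%) |
| Two-sided, enumeration | 13.7-14.2% | 12.0-12.3% | 10.9-11.1% |
| One-sided, normal approximation | 15.9-16.5% | 13.1-13.6% | 10.8-11.2% |
| One-sided, enumeration | 17.0-17.6% | 14.8-15.2% | 12.5-12.9% |

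**What those ceilings mean.** The less sensitive test finds (ψ − 0.10)/2 of the tumor regions that the other misses. At 14% discordance that is 2%, about two regions in 100. At 17.6% it is 3.8%. For comparison, conditionally independent readings at 65% and 75% would disagree in 0.65 × 0.25 + 0.35 × 0.75 = 42.5% of regions.

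**Power for a 10-point sensitivity difference, n = 96, at assumed discordance:**

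| | V = 1 | V = 1.22 | V = 1.488 |
|---|---|---|---|
| ψ = 20%, two-sided | 59% | 51% | 43% |
| ψ = 30%, two-sided | 43% | 37% | 31% |
| ψ = 20%, one-sided | 71% | 64% | 56% |
| ψ = 30%, one-sided | 56% | 49% | 43% |

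**Specificity, n = 140-144, two-sided, normal approximation.** The ceiling is 18.1-18.7% (V = 1), 14.9-15.3% (V = 1.22) or 12.3-12.6% (V = 1.488). Enumeration adds about one point.

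**All 240 regions.** The two-sided ceiling would be 30.9%, 25.4% or 20.9% for the three values of V, but 240 cannot be the denominator for sensitivity.

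**The case against.** The strongest reply is that nothing in the documents contradicts the 80%. The plan cites a published method for clustered McNemar power; very high PET-MRI agreement would deliver the figure; and the 1.22 is borrowed from a single-modality calculation. This stands to the extent that the fault is an unstated assumption and not a demonstrated error. The citation supplies a method but not the inputs, and the ceilings of 12.5-14% two-sided and 16-18% one-sided use no clustering factor at all.

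A reader might infer that 80% is out of reach on the plan's own VIF convention, because the normal approximation stops at 73-75%. That is not supported. With 64-67 effective pairs and only 6-7 expected discordant pairs the approximation is weak. At the minimum discordance, enumeration gives 89-91% for the uncorrected test and 63-67% for the continuity-corrected or exact test. The answer depends on the version of the test, which the plan does not specify.

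A reader might also infer that all 240 regions were used by mistake. The documents do not show how the figure was obtained.

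It is also fair that the sentence may cover more than PET vs MRI sensitivity. Joint PET/MR comparisons may have lower discordance, because the joint reading follows the separate ones, and the specificity claim is attainable. Finally, this is a secondary objective: the primary objective is estimation, the ROC comparison is separate, and no sample size or decision rule is shown to rest on the 80%.

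**Conclusion.** The point holds for PET vs MRI sensitivity. With 96-100 tumor-bearing regions, 80% power for 65% vs 75% exists only if the two readings are almost nested. That is a strong assumption for two readers blinded to each other, in a plan that also asks whether combining the tests improves on either alone, and it is stated nowhere. Any inflation for clustering tightens it further.

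The conclusion rests on the plan's 40% prevalence and its 10-point difference. The 20% and 30% discordance rates, and the use of 1.22 for a paired difference, are assumptions made here to show size. The conclusion does not extend to specificity or to the joint readings, and it does not establish a calculation error.

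**What to change.** Delete the single 80% claim. State instead that PET vs MRI differences in sensitivity and in specificity will be reported with cluster-adjusted 95% confidence intervals, on separate denominators of about 96 and 144 regions.

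If a power statement is kept, give it separately for sensitivity and specificity, with the assumed discordance and its justification, the sidedness, the version of McNemar's test, the VIF convention and the resulting detectable difference. Give the joint PET/MR comparisons their own discordance.

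For illustration only, two-sided differences detectable with 80% power at an assumed 20-40% discordance:

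| | No clustering | 1.22 on variance | 1.22 on SE |
|---|---|---|---|
| Sensitivity, n = 96 | 13-18 points | 14-20 points | 15-22 points |
| Specificity, n = 144 | 10-15 points | 11-16 points | 13-18 points |

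The 20-40% range has no source in the documents and should not enter the protocol without one. Its favourable end is itself lopsided: at 20% discordance and 15.3 points the discordant cells are 17.7% and 2.3%. Intervals avoid the need for such an assumption and are the simpler choice.

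The cost is a wording change in Section 14.0 and a less favourable stated figure for a secondary objective. No extra patients are needed.
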